- **Transient and persistent lesions:** the appearance of new lesions that do not qualify as a flare will be recorded as new transient or new persistent lesions. Transient new lesions are defined as new lesions that heal within 1 week. Persistent new lesions are defined as new lesions that last more than 1 week.
- **Treatment failure:** absence of DC with oral prednisone 1.5 mg/kg/day for a minimum of 3 weeks, or flare between DC and CRmin that is not controlled by a prednisone dose that is 2 dose levels above the dose at which the flare is observed and that is at least 0.3 mg/kg qd (refer to [Table 3](#)), or the occurrence of an SAE considered related to prednisone by the investigator.

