Complete remission on minimal therapy (CRmin)	The absence of new and established lesions completely healed while the participant is receiving prednisone therapy at ≤ 10 mg/day for at least 2 months (8 weeks).
Complete remission off prednisone therapy (CROff)	The absence of new and established lesions completely healed while the participant is receiving no prednisone therapy (or the equivalent) for at least 2 months (8 weeks).
Disease control (DC)	The absence of new lesions and the start of healing of established lesions.
Disease progression	Increase of ≥ 5 points in the PDAI activity score, observed at any post-baseline visit before DC.

	Statistical Analysis Plan	
ARGX-113-1904	Final analysis	Final 2.0 of 22NOV2023

End of consolidation (EoC)	The time at which no new lesions have developed for a minimum of 2 weeks and approximately 80% of lesions have healed.
Flare	Appearance of 3 or more new lesions in a 4-week period that do not heal spontaneously within 1 week or the extension of established lesions, in a participant who had achieved DC.
Treatment failure	Absence of DC with oral prednisone 1.5 mg/kg/day for a minimum of 3 weeks, or flare between DC and CRmin that is not controlled by a dose that is 2 dose levels above the dose at which the flare is observed and that is of at least 0.3 mg/kg qd, or the occurrence of an SAE considered related to prednisone by the investigator.

	Statistical Analysis Plan	
ARGX-113-1904	Final analysis	Final 2.0 of 22NOV2023

TABLE OF CONTENTS

Statistical analysis plan	1
Signature page.....	2
Protocol history	3
List of abbreviations	4
Definition of terms	7
Table of Contents.....	9
1. Introduction	13
1.1 Study objectives.....	13
1.2 Study design	14
1.3 Expected sample size.....	15
1.4 Software.....	15
1.5 Validation model	15
2. General methodology.....	16
2.1 Analysis sets	16
2.1.1 Analysis sets	16
2.1.2 As planned versus as actual analysis.....	16
2.2 Phases and time points.....	17
2.2.1 Analysis Phases and Periods	17
2.2.2 Baseline and change from baseline	18
2.2.3 Relative day	18
2.2.4 Analysis visits	19
2.2.5 Worst-case	21
2.3 Imputation and rounding rules.....	21
2.3.1 Missing values	21
2.3.2 Handling partially or completely missing dates in calculations.....	22
2.3.3 Values below or above a threshold	22
2.3.4 Rounding of derived variables	22
2.3.5 Outliers	22
2.4 Presentation of results.....	23
2.4.1 Calculation of descriptive statistics and percentages	23
2.4.2 Presentation of treatments	24

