4.1.2.3 OTHER SECONDARY ENDPOINTS (NOT ALPHA CONTROLLED)

All other secondary endpoints will be analyzed using the mITT population. Analyses related to data in the period after an event (CRmin, DC) can only be performed in participants with that event.

1. Proportion of PF participants who achieve CRmin within 30 weeks: same derivation as for the primary endpoint (composite strategy) but then for PF participants.
2. Time to CRmin in PV, PF and all participants: same derivation as third key secondary endpoint (composite strategy) but using date of achieving CRmin. Time to CRmin is defined as the time to the moment that the participant achieves CRmin status defined as complete remission while receiving prednisone therapy at 10 mg/day or less for at least 8 weeks, based on the assessment of the investigator. The 8-week period with minimal prednisone necessary to confirm CRmin is included as part of this time period. For example, a participant that achieves complete remission with prednisone ≤ 10 mg/day at week 15 for the first time and maintains this status for 8 weeks will have a time to CRmin of $15 + 8 = 23$ weeks.
3. Proportion of participants achieving DC in PV, PF and all participants (composite strategy)
4. Proportion of participants achieving CR in PV, PF and all participants (composite strategy)

For all subsequent secondary endpoints a treatment policy strategy is applied ignoring ICEs.

5. Proportion of treatment failures as assessed by the investigator in PV and in all participants. Specific reasons for treatment failure can be derived as follows in following order:
 - absence of DC: if participant didn't achieve DC as assessed by the investigator
 - prednisone related SAE: occurrence of an SAE after DC considered related to prednisone by the investigator
 - flare: if previous 2 reasons are not applicable, the reason must be a flare between DC and CRmin that is not controlled by a prednisone dose that is 2 dose levels above the dose at which the flare is observed and that is a least 0.3mg/kg qd

Failure is defined for the whole treatment phase.
6. Number of flares in PV and in all participants: count number of flares as assessed by the investigator. A new flare only emerges after a new DC. Number of flares are counted over the whole treatment + follow-up phase, between first DC and CRmin (or end of treatment period for participants without CRmin) and after CRmin. The initial flare at baseline (if applicable) is not counted.

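### The SAP's rule for treatment-failure reasons can never label a failure as a prednisone-related SAE when the only qualifying event is such an SAE before disease control

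*SAP*

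**What the plan says.** Treatment failure has three components in both documents. Protocol section 1.1 (Definitions of Clinical Terms), repeated in section 10.12, begins with "absence of DC with oral prednisone 1.5 mg/kg/day for a minimum of 3 weeks". It then gives a flare between DC and CRmin that is not controlled at a specified higher dose. The third component, in the wording of the SAP's Definition of terms, is "or the occurrence of an SAE considered related to prednisone by the investigator". Neither document ties that SAE to DC. SAP section 1.2 likewise counts participants with a prednisone-related SAE as treatment failures without mentioning DC.

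SAP section 4.1.2.3, item 5, concerns the "Proportion of treatment failures as assessed by the investigator in PV and in all participants". It adds: "Specific reasons for treatment failure can be derived as follows in following order". The three reasons are:

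1. "absence of DC: if participant didn't achieve DC as assessed by the investigator"
2. "prednisone related SAE: occurrence of an SAE after DC considered related to prednisone by the investigator"
3. "flare: if previous 2 reasons are not applicable, the reason must be a flare between DC and CRmin", followed by the dose condition from the definition.

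Section 8.1 lists the resulting reason tabulations as Table 14.2.1.3.4.2 (PV) and Table 14.2.1.3.4.4 (PV+PF). SAP section 6.1, which lists changes from the protocol, does not mention a change to the failure components.

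**The concern.** The derivation departs from the definition in three places. Reason 1 drops the dose and duration condition. Reason 2 gains a restriction to the period after DC. Reason 3 is assigned by elimination and needs no observed flare. Together these can give a participant a reason that the definition does not support, while the criterion actually met goes uncounted.

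The split of reasons is of interest because the programme seeks a prednisone-sparing effect. Readers will use it to separate failure through steroid toxicity from failure through lack of efficacy. The period that the SAE reason leaves out includes the initial prednisone escalation, which protocol section 6.8.1 places before DC.

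**Working it through.** The plan states no figure here, so there is none to reproduce. The check applies the ordered rule to every combination of the facts that bear on failure, and compares the assigned label with the criteria met under the definition.

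Inputs:
- DC never reached or reached (SAP 4.1.2.3, item 5, reason 1).
- Prednisone-related SAE: none, before DC only, after DC only, or both (reason 2 and the definitions).
- Uncontrolled flare between DC and CRmin: yes or no. It is possible only once DC has been reached.
- At least 3 weeks at 1.5 mg/kg/day: yes or no. It matters to the definition only if DC is never reached.

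Rule: no DC gives absence of DC; otherwise an SAE after DC gives prednisone SAE; otherwise flare.

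The patterns that meet at least one criterion of the definition are:

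| DC | Prednisone-related SAE | Other criterion | Criteria met | SAP label |
|---|---|---|---|---|
| Never | Yes | 1.5 mg/kg/day for 3 weeks not given | SAE | Absence of DC (**not met**) |
| Never | None | 1.5 mg/kg/day for 3 weeks given | Absence of DC | Absence of DC |
| Never | Yes | 1.5 mg/kg/day for 3 weeks given | Absence of DC, SAE | Absence of DC |
| Reached | None | Uncontrolled flare | Flare | Flare |
| Reached | Before only | No such flare | SAE | Flare (**not met**) |
| Reached | Before only | Uncontrolled flare | SAE, flare | Flare |
| Reached | After only | No such flare | SAE | Prednisone SAE |
| Reached | After only | Uncontrolled flare | SAE, flare | Prednisone SAE |
| Reached | Both | No such flare | SAE | Prednisone SAE |
| Reached | Both | Uncontrolled flare | SAE, flare | Prednisone SAE |

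Of these 10 patterns, 4 have one criterion met and the matching label. Another 4 have two criteria met, and the rule shows one of them. The remaining 2 (4 + 4 + 2 = 10) carry a label whose criterion was not met. In both, the only criterion met is an SAE before DC.

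Both can occur in practice. For the first, take as an illustration a prednisone-related SAE in week 3 at 0.75 mg/kg/day in a participant who never reaches DC. The second requires the participant to stay in the trial after the SAE. Protocol section 4.1 and SAP section 1.2 make early rollover optional in that situation, so DC can follow. Such a participant could be tabulated as failing through flare while contributing none to the flare counts in items 6 and 8 of the same SAP section.

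**The case against.** The strongest defence is that a single-reason table needs an order of precedence, and ranking absence of DC first is legitimate. That stands for the overlaps. A participant who had 3 weeks at 1.5 mg/kg/day without DC and also had a prednisone-related SAE meets two criteria, and showing the first is a choice rather than an error. Precedence does not explain the dropped dose condition, the added timing limit or a flare assigned without one being recorded.

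The second defence is that little depends on the rule. This is also largely right. Failure status is the investigator's assessment, so the rule does not enter the failure proportion or its CMH test. The endpoint is not alpha controlled, and neither reason table is marked topline. Prednisone sparing is tested through the normalised cumulative prednisone dose.

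A reader might infer several stronger things that the documents do not support:
- That every prednisone-related SAE before DC is filed under absence of DC. Participants who later reach DC leave that branch; without a further SAE after DC they go to flare.
- That steroid harm is hidden. Serious prednisone-related TEAEs have a line in the adverse event overview and their own Table 14.3.1.7. All prednisone-related TEAEs are in Table 14.3.1.10, a topline output. None of these depends on DC. They do not, however, say why a participant failed, so they do not correct the reason table.
- That the rule is blind exactly when doses are highest. Under protocol section 6.8.1 an escalated dose is held until 2 weeks after DC, and the dose rises again at a flare.
- That placebo is affected more. Nothing in the documents establishes a direction.

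**Conclusion.** The point holds in a narrow form: the derivation in SAP 4.1.2.3, item 5, is wrong as written because it contradicts the definition it is meant to break down. Failures that qualify only through a prednisone-related SAE before DC are missing from the SAE row of the two reason tables and are added to absence of DC or to flare.

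The number affected is unknown, because the documents give no rate of prednisone-related SAEs before DC. It could be zero. The importance is minor.

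The conclusion assumes that DC in reason 1 is judged over the whole treatment phase, the period over which the same item defines failure. If DC were judged only up to the date of failure, participants who reach DC later would move from flare to absence of DC. The SAE reason would still be unavailable to them.

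**What to change.** Bring item 5 into line with the definition that both documents already contain:

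- Delete the restriction to the period after DC from the SAE reason.
- Apply the definition's own dose and duration condition to absence of DC.
- Require a recorded uncontrolled flare between DC and CRmin for the flare reason.
- Add an other/undetermined category.
- Where a participant meets more than one criterion, report all of them as non-exclusive counts, so that no order of precedence is needed. Simply moving the SAE to first place would mask genuine non-response in the overlapping cases.

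This changes no clinical rule and no failure status. Protocol section 8.2 has the investigator record daily prednisone dose, flare and treatment failure, and section 8.4.4 records event onset and relationship to corticosteroids. The cost is revised SAP wording, a derivation of time spent at 1.5 mg/kg/day from the dosing records, and possibly a few investigator-assessed failures that land in the undetermined category.

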4.1.3 Presentation of results and statistical analysis

Wherever the stratification factors will be used in the efficacy analyses, the eCRF values of these will be used and not the ones coming from the randomization. Also for participants randomized without disease status, disease severity and body weight stratification, i.e. Japanese and PF participants, these factors will be derived from the eCRF in order to include these participants in the statistical models.

For the analysis of the PF only population, all stratified models/tests for binary and survival endpoints will only be stratified by the following 2 strata: relapsing vs. newly-diagnosed.

Examples of SAS code for the statistical analysis procedures are provided in Appendix 9.1.5.

	Statistical Analysis Plan	
ARGX-113-1904	Final analysis	Final 2.0 of 22NOV2023

Frequency tabulations will be provided of the percentage of PV participants having achieved CRmin within 30 weeks (primary endpoint). The table will be repeated for subgroups including treatment differences in proportions with 95% Wald CI, and overall (PV+PF participants).

A stratified CMH test will be calculated with the stratification factors of disease status, disease severity, and body weight at randomization; the strata-adjusted difference in proportions with the Klingenberg midpoint and 95% confidence interval and 2-sided CMH test p-value will be provided as well as an adjusted common OR with its 95% confidence interval. Homogeneity of the odds ratios will be tested by means of a Breslow Day test with Tarone's adjustment.

A supplementary analysis using the treatment policy strategy will be done for PV participants and overall.

The supplementary landmark analysis at week 30 will be performed on the mITT population for PV participants and overall using the stratified CMH test.

Summary statistics on NCPD, cumulative prednisone dose, number of days and proportion of days with prednisone equivalent dose ≤ 10 mg will be provided for PV participants and an ANCOVA model with factors for treatment and the stratification variables will be applied on NCPD over the whole treatment phase only. Least square (LS) means and standard error (SE) with 95% 2-sided CI for placebo and efgartigimod will be reported, along with the difference in LS means of IMP vs placebo (with SE), 95% 2-sided CI, and 2-sided p-value. A non-parametric stratified Mann-Whitney test will be performed as sensitivity for PV participants. The 2-sided p-value resulting from this hypothesis test will signify whether the null hypothesis that the distributions of the NCPD for both treatment arms are identical can be rejected. The test will be conducted at a significance level of $\alpha=0.05$. A supplementary analysis using the treatment policy strategy applying the same ANOVA model will be done.

The table with summary statistics on NCPD will be repeated by subgroups, for PF participants and overall.

Time to CR and Time to DC will be descriptively presented with median times, quantiles and number and percentage of participants censored and with event. In addition, Kaplan-Meier survival plots by treatment arm will be produced (as in-text figures only). Both treatment groups will be compared using the stratified Fleming-Harrington weighted logrank statistic FH (1,0). Also the Cox proportional hazard model will be used: the model will include treatment as fixed effects and stratification factors as covariates. The HR for efgartigimod vs. placebo will be provided, along with the associated 95% 2-sided Wald-type CI and 2-sided p-value. The table will be produced for PV participants and overall. The descriptive statistics will also be presented by subgroups.

Duration of CRmin and other 'time to event' parameters of the 'other secondary endpoints' in section 4.1.2.3 will be descriptively presented and treatment groups will be compared using the logrank statistic.

	Statistical Analysis Plan	
ARGX-113-1904	Final analysis	Final 2.0 of 22NOV2023

Frequency tabulations will be provided for the percentages of treatment failure and its different reasons. Failure rates will be compared using the same CMH-test as for the primary endpoint analysis.

Proportion of participants achieving DC and CR and proportion of participants with flare will be tabulated and treatment groups will be compared using the same CMH-test as for the primary endpoint analysis.

Descriptive statistics for PDAI on absolute values, changes from baseline and percent changes from baseline will be calculated per timepoint. Results will be presented separately for observed data and LOCF imputed data. Changes from baseline on LOCF imputed data will be compared between treatment arms at each analysis visit using an ANCOVA model with factors for treatment, baseline value and the stratification variables. Least square (LS) means and standard error (SE) with 95% 2-sided CI for placebo and efgartigimod will be reported, along with the difference in LS means of IMP vs placebo (with SE), 95% 2-sided CI, and 2-sided p-value.

The number of flares will be descriptively presented and analyzed by the same ANCOVA model as for the NCPD analysis. Time to the first flare will be presented and analyzed in the same way as time to CR or time to DC, however using the logrank statistic.

Frequency tabulations will be provided for the percentages of participants within each outcome of QoL questionnaire items (ABQOL and EQ-5D-5L). Additionally cumulative percentages (starting with the best outcome result) will be calculated. Descriptive statistics will be provided for the total ABQOL score and for the EQ-5D-5L VAS score. Changes from baseline will be analyzed by means of a mixed model for repeated measurements (MMRM). The model will include treatment, visit and treatment by visit interaction terms as fixed effects, with baseline value, interaction of baseline value with visit, and stratification factors as covariates. Within-subject correlation will be modeled by assuming an unstructured covariance matrix (UN) for the error terms and Kenward-Roger degrees of freedom method will be used. Least square means and SE with 95% 2-sided CI for placebo and efgartigimod will be reported, along with the difference in LS means of IMP vs placebo (with SE), 95% 2-sided CI, and 2-sided p-value.

If the default Newton–Raphson algorithm used by SAS PROC MIXED fails to converge, the following will be tried to avoid lack of convergence while maintaining an unstructured variance:

- A. The Fisher scoring algorithm (via the SCORING = 5 option of the PROC MIXED statement) will be used to obtain the initial values of covariance parameters.
- B. If the above fails, the no-diagonal factor analytic structure will be used which effectively performs the Cholesky decomposition via the TYPE=FA0(V) option of the REPEATED statement, where V is the total number of distinct visits in the response vector (counting only rows where all model components are non-missing).
- C. If all the above fails, the variance-and-correlations parameterization will be attempted using TYPE =UNR.

	Statistical Analysis Plan	
ARGX-113-1904	Final analysis	Final 2.0 of 22NOV2023

In the rare case where all the above fails, the following covariance structures will be tested for convergence (in order): toeph, arh(1), csh, toep, ar(1) and cs. However, if one of these simpler covariance structures is used, this needs to be implemented in combination with sandwich variance estimator (EMPIRICAL option).

Descriptive statistics will be provided for the C-GTI scores AIS and CWS; treatment groups will be compared using the same ANCOVA model and stratified Mann-Whitney test as for the NCPD analysis. C-GTI will be analysed on complete cases: i.e. participants with C-GTI at least at baseline and post-baseline. Participants where first post-baseline GTI improvements/worsening have not been obtained with respect to the baseline moment but with respect to a later moment (i.e. no GTI assessment at baseline visit) are excluded from analyses and are only listed.

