4.1.2.2 KEY SECONDARY ENDPOINTS (ALPHA CONTROLLED)

The following key secondary endpoints, which will be tested in the mITT population in hierarchical order (see section 4.1.4), are defined as:

- 1) The proportion of PV+PF participants that have achieved CRmin within 30 weeks using the same stratified CMH as for the primary endpoint. As this first key secondary endpoint is similar to the primary endpoint, the same approach for handling the main ICEs (both composite strategy and treatment policy strategy), as suggested for the primary analysis, will be applied.
- 2) Normalised cumulative Prednisone dose (NCPD, mg/kg/day) over the whole planned treatment phase in PV participants, will be analyzed by an analysis of covariance (ANCOVA) model to compare both treatment groups. Only actual administrations of prednisone are considered (not as scheduled). The model will include treatment and the stratification variables will be considered as factors.

Main intercurrent events are handled using the hypothetical strategy, that is, as follows:

- Intercurrent medications (see section 3.4.2): stop calculating cumulative dose after ICE. In case 'immunosuppressants for at least 4 weeks in total' is the ICE, use end of the 4 weeks IC medication as stop for cumulative dose calculation. In case ‘tetracyclines for at least 2 weeks in total' is the ICE, use end of the 2 weeks IC medication as stop for cumulative dose calculation. In case ‘IV or IM corticosteroids ' is the ICE, use the first day of this IC medication as stop for cumulative dose calculation.
- Discontinuation of IMP before CRmin due to lack of efficacy: stop calculating cumulative dose after this ICE.

Details on the derivation of intercurrent events are provided in Appendix 9.1.

	Statistical Analysis Plan	
ARGX-113-1904	Final analysis	Final 2.0 of 22NOV2023

A non-parametric stratified Mann-Whitney test will be performed as sensitivity analysis.

A supplementary analysis for this secondary endpoint will use the ‘treatment policy strategy’ where the occurrence of the intercurrent event is considered irrelevant: NCPD is calculated regardless of whether or not the intercurrent event occurs.

3) Time to CR in PV participants, calculated as the difference between the first date CR was achieved and the first IMP administration date.

Time to CR (days) = date (first CR) - first IMP date + 1

Main intercurrent events are handled as follows (composite strategy):

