- Intercurrent medications (see section 3.4.2) before CR: participant is assumed to not reach CR until the theoretical end of the study and is censored at day 218.
- Discontinuation of IMP before CR due to lack of efficacy: participant is assumed to not reach CR until the theoretical end of the study and is censored at day 218.

Participants without any disease assessment are censored at day 1. Participants with disease assessment but not achieving CR in the period from Day 1 to Day 218 and without intercurrent event in that period are censored at the earliest of day 218 and the end of treatment + FU phase.

A supplementary analysis for this secondary endpoint will use the ‘treatment policy strategy’ where the occurrence of the intercurrent event is considered irrelevant: Time to CR is calculated regardless of whether or not the intercurrent event occurs.

4) Time to DC in PV participants, calculated as the difference between the first date DC was achieved and the first IMP administration date. Similar calculations, ICE handling and censoring rules are applied as for ‘time to CR’ (composite strategy).

A supplementary analysis for this secondary endpoint will use the ‘treatment policy strategy’ where the occurrence of the intercurrent event is considered irrelevant: time to DC is calculated regardless of whether or not the intercurrent event occurs.

Both time to event endpoints will be statistically evaluated using the stratified Fleming-Harrington weighted logrank statistic FH (1,0), with the stratification factors disease status, disease severity, and body weight at randomization. For both, Kaplan-Meier survival plots by treatment arm will be produced (as in-text figures only).

5) NCPD over the whole planned treatment phase in all participants: same derivation as second key secondary endpoint (composite strategy and treatment policy strategy) but for all participants.

6) Time to DC in all participants: same derivation as fourth key secondary endpoint (composite strategy) but for all participants.

7) Time to CR in all participants: same derivation as third key secondary endpoint (composite strategy) but for all participants.

	
Statistical Analysis Plan
	

ARGX-113-1904
	
Final analysis
	
Final 2.0 of 22NOV2023

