4.1.4 Fixed-Sequence testing procedure

To control the type I error for the primary and secondary endpoints (alpha controlled), the primary efficacy endpoint will be tested at the 5% 2-sided alpha level and will act as gatekeeper for the testing of secondary endpoints. The primary endpoint and secondary endpoints will be tested in a strict hierarchical order as listed below to control the type I error (for definitions see section 4.1.2.1 and 4.1.2.2). If a certain endpoint turns out to be non-significant at the 5% significance level, subsequent endpoints will no longer be evaluated.

1. Primary endpoint: the proportion of PV participants who achieve CRmin within 30 weeks using composite strategy approach
2. Proportion of PV+PF participants that have achieved CRmin within 30 weeks using composite strategy approach
3. NCPD in PV participants using hypothetical strategy approach
4. Time to CR in PV participants using composite strategy approach
5. Time to DC in PV participants using composite strategy approach
6. NCPD in PV+PF participants using hypothetical strategy approach
7. Time to CR in PV+PF participants using composite strategy approach
8. Time to DC in PV+PF participants using composite strategy approach

The individual per-endpoint tables will only show unadjusted p-values. A fixed-sequence testing procedure table will be produced. This table will show both unadjusted p-values and p-values adjusted for multiplicity. For a given endpoint, the adjusted-for-multiplicity p-value is calculated as the maximum between its unadjusted p-value and the highest of all unadjusted p-values tested before.

	Statistical Analysis Plan	
ARGX-113-1904	Final analysis	Final 2.0 of 22NOV2023

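### The alpha-controlled PV+PF analyses have no disease-type term in the SAP text, and the documents disagree on how PF participants were randomised

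*SAP*

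**What the plan says.** SAP 4.1.4 tests eight hypotheses in order. Positions 2 (CRmin), 6 (NCPD), 7 (time to CR) and 8 (time to DC) are in PV+PF participants; position 6, for example, reads "NCPD in PV+PF participants using hypothetical strategy approach". SAP 6.1 records that positions 6 to 8 were added to the sequence by the SAP.

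Each pooled test reuses the PV method in SAP 4.1.2.2 and 4.1.3:

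- CRmin: "The proportion of PV+PF participants that have achieved CRmin within 30 weeks using the same stratified CMH as for the primary endpoint".
- NCPD: "The model will include treatment and the stratification variables will be considered as factors". For the pooled population: "NCPD over the whole planned treatment phase in all participants: same derivation as second key secondary endpoint". SAP 4.1.3 repeats the model: "an ANCOVA model with factors for treatment and the stratification variables will be applied on NCPD over the whole treatment phase only".
- Time to CR and time to DC: a Fleming-Harrington FH(1,0) test "with the stratification factors disease status, disease severity, and body weight at randomization".
- The supportive Cox model, which SAP 6.1 lists as an extra analysis outside alpha control: "the model will include treatment as fixed effects and stratification factors as covariates".

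In the efficacy plan, disease type appears as a subgroup factor (SAP 4.1.5) and as a population definition, but not as a model term or stratum. The example SAS code in SAP 9.2 is blacked out, so this can be established from the text only.

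On randomisation, SAP 4.1.3 describes "participants randomized without disease status, disease severity and body weight stratification, i.e. Japanese and PF participants" and derives the three factors for them from the eCRF. Protocol 4.1 limits the stratification to non-Japanese participants, which includes non-Japanese PF. The synopsis (protocol 1.1) and SAP 1.2 describe the three-factor stratification with no exemption.

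**The concern.** PV and PF are distinct diseases, and PF is up to 30 of 213 participants (14.1%). If outcome differs between them, a pooled analysis without a disease-type term leaves that difference in the residual. Power at four confirmatory tests may then be lower than it need be.

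How the loss arises depends on how PF was randomised. If PF had its own list, the arms are balanced on disease type by design. The treatment estimate is then as precise as with the term, but the model-based standard error is too large and the test is slightly conservative. If PF shared the three-factor strata with PV, disease type is balanced only by chance. Test size is then nominal, but the estimate itself is less precise. The documents do not settle which case applies.

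**Working it through.** **Inputs.** Protocol 9.3: two-sided 5%; 34% versus 11% with 183 PV for 95% power. SAP 1.3: 183 PV and up to about 30 PF, each 2:1, total 213. Three two-level factors.

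**The plan's own figure.** With 61 placebo and 122 efgartigimod PV participants at 11% and 34%, the pooled normal approximation gives 94.7% power and the exact chi-square 95.0%. The stated 95% reproduces, so N and allocation are read correctly.

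**Degrees of freedom, PV+PF NCPD ANCOVA.**
- As written: 213 − (1 intercept + 1 treatment + 3 factors) = 208.
- With a PV/PF main effect: 207.
- The two-sided 5% critical t moves from 1.97143 to 1.97149.

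**Analytic size of the loss.** Let d be the PF-PV difference in residual SD units. Omitting the term inflates the model standard error by sqrt(1 + p(1 − p)d²), with p = 30/213 = 0.141 and p(1 − p) = 0.121:
- d = 0.25: sqrt(1.0076) = 1.004
- d = 0.5: sqrt(1.0303) = 1.015
- d = 1: sqrt(1.121) = 1.059

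With 142 versus 71 participants, the standard error of the treatment difference is sqrt(1/142 + 1/71) = 0.1454 SD. An assumed effect of 0.42 SD gives 0.42/0.1454 = 2.89, and power of 82.0% with the term. At d = 1 without the term, power is 78.8% with a separate PF list (size 3.8%) and 77.5% with shared strata.

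**Simulation check.** 30,000 runs per power scenario, permuted blocks of 6, residual SD 1, factor effects 0.3, 0.4 and −0.2. The block size, these effects, 0.42 SD and every d are assumptions. Power as planned versus with disease type:

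| d (SD) | Separate PF list | Shared strata |
|---|---|---|
| 0 | 82.0% vs 81.9% | 81.8% vs 81.6% |
| 0.25 | 82.1% vs 82.3% | 81.9% vs 81.9% |
| 0.5 | 80.9% vs 81.7% | 80.8% vs 81.7% |
| 1 | 78.7% vs 82.0% | 77.7% vs 82.0% |

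Planned test size falls from 5.1% at d = 0 to 3.7% at d = 1 with a separate list, and stays at 4.9–5.3% with shared strata. A variant that exempts about 9 PV and 2 PF Japanese participants, and also tries PF and Japanese participants pooled on one list, gives the same picture: about 80.4% versus 81.3% at 0.5 SD, and 77.7% versus 81–83% at 1 SD.

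**CMH, position 2.** 20,000 runs, PV rates 34% and 11%, planned versus one PF stratum:

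| PF odds relative to PV | Separate PF list | Shared strata |
|---|---|---|
| ×1/3 | 96.0% vs 96.2% | 95.8% vs 96.0% |
| ×1 | 97.3% vs 97.2% | 97.3% vs 97.1% |
| ×3 | 97.8% vs 97.9% | 97.8% vs 98.0% |
| ×6 | 97.4% vs 98.0% | 96.8% vs 97.8% |

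**FH(1,0), positions 7 and 8.** 3,000 paired runs; assumed hazard ratio 1.7, placebo median 150 days, censoring at day 218, 15% early dropout; planned versus one PF stratum:

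| PF hazard relative to PV | Separate PF list | Shared strata |
|---|---|---|
| ×0.5 | 75.2% vs 75.8% | 76.0% vs 76.4% |
| ×1 | 78.0% vs 77.3% | 78.9% vs 78.2% |
| ×2 | 76.7% vs 77.5% | 78.6% vs 79.7% |
| ×3 | 75.8% vs 78.3% | 75.6% vs 77.4% |

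The standard error of a paired difference is about 0.3–0.4 points, so several of these differences are near the noise.

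**The case against.** The strongest reply is that nothing here is wrong, only less than optimal. The ANCOVA gain exceeds 1 point only at an assumed 1 SD difference, and nothing in the documents supports a difference of that size. Protocol 2.1 says PF is managed and monitored like PV, protocol 2.2 says both mucosal and extensive cutaneous lesions heal late, and SAP 6.1 reports no comparable PF control data. The documents give no NCPD SD or effect size, so the power figures are conditional illustrations. That stands, and it is why the point is minor.

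The planned models also follow protocol 9.5.7 and 9.5.8, which carry the PV methods over to PV+PF. PF-only and subgroup analyses are planned, and each pooled test comes after its PV-only counterpart; position 6 is reached only if the first five tests succeed. All of this is true. It limits the consequence but does not supply the adjustment.

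Third, SAP 4.1.3 does not mention a separate PF list; that is an inference, compatible with the separate 2:1 statements for PV and PF. The Japanese exemption was also left out of the main simulations. Both points are fair, but the variant that handles them gives essentially the same power figures.

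Finally, adding the term to the Cox model but not to FH(1,0) would put the hazard ratio and the confirmatory p-value on different adjustment sets. That is a real cost of leaving the FH stratum optional.

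**Conclusion.** The concern holds, as a minor one. The SAP text gives the four alpha-controlled PV+PF tests no disease-type term. The four descriptions of PF randomisation cannot all be true for non-Japanese PF participants. There is no bias and no inflation of type I error.

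For the PV+PF NCPD ANCOVA, the term costs 0.0–0.2 power points if PF and PV do not differ. It gains 0.8–0.9 points at 0.5 SD and 3.3–4.3 points at 1 SD, on an assumed effect of 0.42 SD. The gain is similar under either reading of the randomisation, so the model change need not wait for the wording to be resolved. For CMH and FH(1,0), the balance is too close to call for a firm change.

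**What to change.** 1. In SAP 4.1.2.2 and 4.1.3, add disease type (PV/PF) as a factor in the PV+PF NCPD ANCOVA and in the supportive PV+PF Cox model, keeping the three existing factors. Record this in SAP 6.1 as a departure from protocol 9.5.7 and 9.5.8. Cost: about one sentence in each place and one degree of freedom. Pemphigus type is already collected (SAP 3.2.1).

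2. Optionally, give PF its own stratum in the PV+PF CMH and FH(1,0) tests, or use the two disease-status strata that SAP 4.1.3 already sets for PF-only analyses. If prognosis is equal, this costs 0–0.2 points for CMH and about 0.5–1.5 points for FH(1,0), across runs with one or two PF strata. PF would also lose severity and weight adjustment, although protocol 4.2 says the time at which CRmin is expected varies with body weight. If the stratum is not added to FH(1,0), state that the Cox hazard ratio uses a different adjustment set.

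3. Reconcile protocol 1.1 and 4.1 with SAP 1.2 and 4.1.3, and state whether PF participants were randomised with or without the three factors and whether they had their own list.
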